## Objectives

The following specific aims, directional hypotheses, and research questions are:

**Primary Aim:** To test whether the FamPALcare nursing care intervention could reduce the burden of family caregivers by preventing caregiver depression/anxiety and improve patient HF-related health status and depression/anxiety. The hypotheses and research questions are as follows:

*Aim 1.1* Compared to those in the control group at 3 and 6 months, the caregivers who receive FamPALcare will have significant improvements in home caregiving burden and depression/anxiety scores.

*Aim 1.2* Compared to those in the control group at 3 and 6 months, patients in the FamPALcare group will experience greater improvement in HF-related health and depression/anxiety scores.

**Secondary Aim:** To assess the feasibility and fidelity of the FamPALcare intervention.

*Aim 2.1.* What are the participant recruitment, enrollment, and retention outcomes?

*Aim 2.2.* How helpful the FamPALcare as rated by participants on the anonymous 11-item Helpfulness Questionnaire?

*Aim 2.3.* What is the FamPALcare implementation cost using traditional tabulated cost-minimization analysis?

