## **Statistical Considerations**

### ***Sample Size Calculation***

In this R15, sample size is based on reductions in breathlessness; a significant reduction of 1 SD, was found in the PI's previous interventions on end-stage HF breathlessness. A sample size of 30 (15 per group) is able to detect a reduction of 1.3 SDs with a Type 1 error rate of 0.05 and a power of 0.80 [31-33] To account for an expected 20% attrition (due to HF deaths), three additional families will be recruited to each group. Thus, there will be 18 patient-caregiver dyads per each group (total N=72; 36 patients and 36 caregivers).

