## **Statistical Analysis Plan**

Descriptive statistics (frequencies, means, standard deviations) will summarize the caregiver and patient characteristics and program implementation costs. A generalized linear model (GLM) will test for significant differences between the control and intervention groups in terms of health outcome scores measured at baseline and at 3 and 6 months, controlling for covariate effects. The GLM is the extended version of the general linear model applicable to variables that are not normally distributed and is commonly used in small sample studies [39]. The GLM also provides a post hoc analysis that yields results similar to those of t tests. A strength of GLM is that it also provides repeated data collection time factors in post hoc analyses. A one-tailed group comparisons will be used to test our *a priori* directional hypotheses using the

---

Bonferroni adjustment. [40]. Thus, this post hoc paired comparison between groups can reveal significant differences between outcomes at baseline vs. 3 months and at baseline vs. 6 months. The intent-to-treat statistical approach will be used, as all patients are included in the analysis with imputation means replacement [41]. Data analyses will be conducted using SPSS (version 29).

This study will use a traditional cost accounting method to calculate the cost of implementing FamPALcare. All expenses related to delivering the program will be tabulated. The cost of the clinician delivering the intervention will be calculated from an average of a nurse's hourly salary. The costs of educational materials given to participants in the manual will be tallied and summarized.

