## **Data Management**

### ***Data Collection Methods***

Data will be collected from all patients and caregivers at baseline, 3 months, and 6 months. The analyses file of this project will include repeated questionnaire variables across 3 time points, including caregiver and patients' sociodemographic health data.

To preclude diffusion of treatment across groups, the research nurses working with the intervention group will be different from nurses with the control group. Data collectors are blinded to group. Secure data collection and storage is maintained. A home HF EOLPC checklist is used to assess at 3, 6, and 12 months the home care skills learned by the caregiver and to identify areas that may need reinforcement.

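### Missing scores are to be replaced by a single unnamed mean with no variance correction: depending on which mean is used, the test rejects too often or the effect is understated

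*Combined protocol and SAP*

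**What the plan says.** The Statistical Analysis Plan adopts intent-to-treat and gives one clause on missing data: "all patients are included in the analysis with imputation means replacement". It does not say whether the mean is that of the arm, of the whole sample or of the participant. It gives no adjustment of the standard error or degrees of freedom for filled values, no rule for patients who die, and no sensitivity analysis.

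Loss is expected. The Sample Size Calculation says: "To account for an expected 20% attrition (due to HF deaths), three additional families will be recruited to each group". That gives 18 dyads per arm.

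Each score is measured three times (Data Collection Methods): "Data will be collected from all patients and caregivers at baseline, 3 months, and 6 months". The primary hypotheses under Objectives rest on these scores at 3 and 6 months; for example, "patients in the FamPALcare group will experience greater improvement in HF-related health and depression/anxiety scores".

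The tests are one-tailed, with a Bonferroni adjustment over an unstated number of comparisons, in a generalized linear model with covariates. The contrast is described as follows: a "post hoc paired comparison between groups can reveal significant differences between outcomes at baseline vs. 3 months and at baseline vs. 6 months". This could mean follow-up scores compared between arms, or change from baseline compared between arms.

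**The concern.** A filled mean carries no new information, but software treats it as an observation. What goes wrong depends on the mean:

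- **Own-arm mean.** The difference between arms is unchanged, but the sample size goes up and the standard deviation goes down. The standard error is too small, so there are too many false positives and intervals are too narrow.
- **Mean of both arms.** Both arms receive the same filled value, which pulls them together and understates the effect.
- **Participant's own earlier mean.** The pre-treatment baseline enters the follow-up score and dilutes the effect.

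This bears on the primary comparisons of a small trial that itself predicts the missing data. Because no mean is named, the choice could also be made after the data are seen.

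**Working it through.** **The plan's own figures.** The 18 per arm is 15 + 3, which is also 15 × 1.2. Losing the three extra dyads leaves 15 of 18; 20% of 18 is 3.6. So the check uses k = 3 or 4 lost per arm, leaving m = 15 or 14. (The statement that 15 per group detects 1.3 SD at 0.80 power does not reproduce: a t-test gives 0.93 two-sided and 0.97 one-sided. That is a separate matter, and nothing below uses it.)

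**Inputs from the documents:** 18 per arm, 20% attrition, type I error 0.05, one-tailed group comparison, visits at baseline, 3 and 6 months.

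**Assumptions:** equal loss in both arms, completely at random, all k missing at the tested visit; normal scores with SD 1; a two-sample t-test standing in for the planned model; 0.05 before Bonferroni unless stated.

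**1. Own-arm mean, follow-up scores (exact).** Filling leaves each arm's mean and sum of squares unchanged. The squared standard error is proportional to 1/(18 × 17) instead of 1/(m(m − 1)), so t is inflated by

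f = √[18 × 17 / (m(m − 1))].

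- k = 3: f = √(306/210) = 1.207; reported SE is 1/1.207 = 0.83 of the correct one.
- k = 4: f = √(306/182) = 1.297; reported SE is 1/1.297 = 0.77 of the correct one.

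The true type I error is P(t with 2m − 2 df > c/f), where c is the critical value on 34 df.

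| Nominal one-sided level | c | k = 3 (28 df) | k = 4 (26 df) |
|---|---|---|---|
| 0.05 | 1.691 | P(t > 1.401) = 0.086 | P(t > 1.304) = 0.102 |
| 0.025 | 2.032 | P(t > 1.684) = 0.052 | P(t > 1.567) = 0.065 |
| 0.0125 | 2.345 | P(t > 1.943) = 0.031 | P(t > 1.809) = 0.041 |

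The levels 0.025 and 0.0125 correspond to two and four tests; the plan states no number. Coverage of the 95% interval is 1 − 2 × 0.0517 = 90% (k = 3) and 1 − 2 × 0.0646 = 87% (k = 4).

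Simulation (60,000 trials per setting, correlation between visits 0 to 0.7) gave 0.084 to 0.088 and 0.099 to 0.102, and about the same with baseline as a covariate.

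**2. Own-arm mean, change from observed baseline.** The lost participants' real baselines still vary, so the change scores keep some spread. Simulated type I error is 0.064 to 0.069 (k = 3) and 0.071 to 0.074 (k = 4).

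**3. Mean of both arms.** With equal loss the expected difference is multiplied by m/18, so the shrinkage is k/18: 3/18 = 17% and 4/18 = 22%. Simulated type I error is 0.049 to 0.052. For a true effect of 1.0 SD, 95% interval coverage is 92% (k = 3) and 89% (k = 4).

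**4. Participant's own earlier mean.** Assume the same effect at both follow-up visits. A participant lost before 3 months contributes baseline only (no effect). One lost after 3 months contributes the average of baseline and 3 months (half the effect). Expected 6-month shrinkage is (lost before + ½ × lost after)/18:

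- all lost after 3 months: 1.5/18 = 8% to 2/18 = 11%;
- all lost before 3 months: 3/18 = 17% to 4/18 = 22%.

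Simulated type I error is 0.048 to 0.052.

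**The case against.** The strongest reply is that the harm depends on a reading the plan does not fix.

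- **The contrast.** The plan's wording about baseline against each follow-up visit fits change scores at least as well as follow-up scores. There the excess over 0.05 is roughly half as large (0.064 to 0.074). This stands, so both ranges are given.
- **Bonferroni.** It lowers the nominal level, so 0.086 to 0.102 is not the planned per-test error if several tests are adjusted. This stands too, but the fault remains: the error is about 2.1 to 2.6 times nominal at 0.025.
- **Two of the three readings keep the type I error.** Under equal random loss this is correct. With the mean of both arms, power for 1.0 SD is essentially that of the observed cases (0.850 v 0.849 with 3 lost, 0.825 v 0.823 with 4). The test is hardly affected; the estimate and its interval are.
- **Caregivers.** The clause names patients, and the expected attrition is patient death. A caregiver need not be lost when the patient dies, so applying these figures to the caregiver hypotheses is an inference.

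A reader might infer that the plan doubles the false-positive rate. The documents do not support that as a general statement: it needs own-arm filling, follow-up scores, four lost per arm and an unadjusted 0.05. A reader might also infer that attrition from heart-failure deaths tilts the result towards FamPALcare. If loss is related to health and differs by arm, bias can go either way, and the documents give no figures to size it.

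**Conclusion.** Wrong as written, and more than a missing detail: the plan states a rule for the primary scores, and none of the three usual readings gives both a valid standard error and an undiluted effect.

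Own-arm filling makes the one-sided type I error about 0.064 to 0.102 at a nominal 0.05, depending on the contrast. Filling with the mean of both arms understates the raw effect by 17% to 22%, with interval coverage below 95%. Own-earlier-mean filling understates the 6-month effect by about 8% to 22%. Inflation and shrinkage are alternatives; they do not occur together under these assumptions.

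That a rule with no stated correction treats filled values as observed is an inference, but a fair one. The sizes rest on 3 to 4 of 18 lost per arm at the tested visit, with equal and completely random loss. The own-mean range also assumes an equal effect at both visits.

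**What to change.** Delete the mean replacement from the intent-to-treat sentence and state instead:

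- Participants are analysed by assigned arm, and no missing score is filled with a mean.
- Each score is analysed with a likelihood-based repeated-measures model on all observed baseline, 3- and 6-month values, with group-by-visit effects, the planned covariates and a small-sample correction to the degrees of freedom (Kenward-Roger, if the SPSS version offers it).
- Residuals are checked. For markedly non-normal scores, a suitable transformation or a generalized linear mixed model is used, which keeps the plan's reason for choosing a GLM.
- Deaths and other losses are tabulated by arm and visit.
- How death enters the patient comparison is stated; that choice belongs to the investigators.
- Whether the rule covers caregivers is stated.
- One labelled sensitivity analysis is reported, such as the baseline-adjusted comparison among those with a score.

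**Cost.** New wording and a little more analysis; no new data. Standard errors will be wider than under own-arm filling, which is the correction intended. The model implicitly extrapolates patient scores past death, which is why the handling of death has to be stated.

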## **Data Management**

### ***Data Collection Methods***

Data will be collected from all patients and caregivers at baseline, 3 months, and 6 months. The analyses file of this project will include repeated questionnaire variables across 3 time points, including caregiver and patients' sociodemographic health data.

To preclude diffusion of treatment across groups, the research nurses working with the intervention group will be different from nurses with the control group. Data collectors are blinded to group. Secure data collection and storage is maintained. A home HF EOLPC checklist is used to assess at 3, 6, and 12 months the home care skills learned by the caregiver and to identify areas that may need reinforcement.

### ***Data Handling and Record Keeping***

Data will be stored separately in a locked file at the WVUSON research office. Only selected research staff will have access to the subjects' PHI. Information protection procedures specific to data management and communications are also in place. All subjects and staff are informed that subjects' PHI will not be discussed or placed on the Internet so that incidental disclosure does not occur. Electronic data will be kept in the firewall, password-protected server at the Health Science Center with daily backup. Any staff member who may leave during the project period will have all data access terminated immediately.

## **Ethical Considerations**

### ***Informed Consent Process***

The PI and Co-I will train our recruiters per enrollment and recruitment protocols. Recruitment forms with enrollment scripts and consent forms have been successfully used with HF families in the previous studies. Our research team will review all recruitment, consent, and data forms for the study proposal and submit to the IRB prior to any enrollment. Trained research team members who have completed the NIH-approved Human Subjects Protection certification (CITI) will obtain informed consents. Upon screening for eligibility criteria, with the potential participants' permission, a research nurse will contact the individual and use a script to discuss consent for the study. If the individuals agree to participate in the study, they must verbally indicate that they understand the purpose of the study and their rights as participants. Consent will be documented as a signed form, will be kept in a locked file at the study office, and a copy provided to all participants. All subjects will be encouraged to contact the Human Subjects Committee with any concerns about the informed consent document.

### ***Confidentiality***

Several procedures are established for protecting against the risk of breaking confidentiality. First is the decoupling of all subjects' Protected Health Information (PHI) from all study materials. Data will be de-identified and subjects will be assigned a unique, unidentifiable code number. A list that links the assigned code number to the subjects' PHI, as well as the informed consents, will be stored separately in a locked file at WVUSON research office. Only selected research staff will have access to the subjects' PHI. Information-protection procedures specific to data management, communications, and the electronic environment are also in place. All subjects and staff are informed that subjects' PHI are not to be discussed or placed on the internet so that incidental disclosure does not occur.

---

